- a. **Recruitment, sample description and inclusion/exclusion criteria.** Participants will be recruited through advertisements on social media, paper flyering, advertising on local list-servs, and by peer recruitment. Our lab has successfully attracted over 340 participants to complete our screening measures using these methods in the past year. Interested individuals can contact the laboratory via email or phone call to arrange a phone screen, where we will assess likely eligibility for the study.
 - i. **Inclusion criteria:** A) Between 18 and 35 years of age,
 - ii. **Exclusion criteria:** A) AUDIT Score less than or equal to 14, B) Non-drinker C) positive result on urine drug screen or breathalyzer at the start of any study visit, D) inability to complete MRI (e.g. presence of ferromagnetic objects in body), E) current use of medications that alter the hemodynamic response, such as insulin, F) history of trauma resulting in loss of consciousness longer than 15 minutes, G) for females, pregnancy, H) current (within the last 3 months) use of opioids to avoid acute precipitated withdrawal due to opioid receptor antagonism I) treatment for a DSM5 disorder other than anxiety or depression through therapy J) treatment for a DSM5 disorder through medications, K) greater than 10 uses of illicit substances in the last year.
- b. **Feasibility:** We have recruited 45 participants to our laboratory's studies in the past year and conducted 45 MRI scans. To recruit ~10 participants in one year, we need to recruit 1 participant per month and conduct 2 scans per month. This is well within the capacity of our laboratory operations.

C. Study Design and Research Methods. After completing an informed consent procedure, participants will sign a consent form. They will then complete a psychiatric interview and receive 5 capsules. Participants will return five days later for visit 2. On visit 2, they will complete a medication side-effect questionnaire. If they report side effects that are more

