than mild (i.e. if they report moderate or severe side effects), a medical professional (i.e. nurse or physician) will follow up to confirm that they are ok to complete the MRI and provide care as needed. All participants will complete a breathalyzer and saliva drug test to confirm sobriety. Females will be asked to provide a urine sample for a pregnancy test. Participants will then complete an MRI and the Alcohol Purchase Task. They will be sent home with 5 days' worth of capsules. They will return after 5 days and repeat the same procedures.

- a. Dosing. We will administer doses of naltrexone and placebo. Dosing will be double-blind and counter balanced. Participants will receive 5 capsules on their first visit to take during the week. They will receive 5 additional capsules to take each day of the following week. Naltrexone will be over-encapsulated by the Investigational Drug Service at the School of Pharmacy. Matching placebo capsules will contain methylcellulose powder. Naltrexone will be taken once daily by mouth and ramped up by the following schedule: Monday-25mg, Tuesday-25mg, Wednesday-50mg, Thursday-50mg, Friday-50mg. A study coordinator blind to the contents of the capsules will deliver the capsules to the participant. The Investigational Drug Service will maintain blinding and will track dosage, to be revealed following study completion. Half of participants will receive placebo during week 1 and half will receive placebo during week 2. Remote video monitoring will also be used to assess adherence. Participants will receive a text message on their mobile phones at 9 am each morning reminding them to take the medication and instructing them to upload a video of themselves doing so to a secure data repository (REDCap). A study-provided mobile phone will be available for participants who do not own a mobile phone or who are not willing to use their phone for this purpose (i.e., due to concerns about mobile data cost). The digital timestamps of these videos will subsequently be extracted, and their contents reviewed, to verify that the participant ingested the medication at the instructed time. Other studies of non-treatment-seeking individuals have reported success with remote video monitoring (DeWorsop et al. 2016).

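### No pregnancy test is specified before the first capsules are dispensed at visit 1, although pregnancy excludes from the whole study

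*Combined protocol and SAP*

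**What the plan says.** Section IV.B.a.ii lists pregnancy among the general exclusion criteria: "G) for females, pregnancy". Section IV.D.b, under the MRI risks, goes further. It bars women who are pregnant or plan to become pregnant during the study from taking part, and it removes from the study anyone whose test is positive or uncertain. Both statements concern participation, not only scanning.

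Eligibility is first considered by telephone. Section IV.B.a has interested people contact the laboratory to "arrange a phone screen, where we will assess likely eligibility for the study". No test is mentioned there.

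Section IV.C gives the visits. After consent at visit 1, "They will then complete a psychiatric interview and receive 5 capsules". Section IV.C.a confirms that these are for use straight away: "Participants will receive 5 capsules on their first visit to take during the week". Then "Participants will return five days later for visit 2", and it is in the visit 2 sequence, before the MRI, that the first pregnancy test appears: "Females will be asked to provide a urine sample for a pregnancy test". A second set of capsules follows, and for the third visit "They will return after 5 days and repeat the same procedures".

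The only timing rule for the test is in section IV.D.b, which sets it at no more than 24 hours before each MRI. The measures for minimizing naltrexone risk in section IV.D.d.iii are video monitoring of adherence, a lower starting dose and a side-effect questionnaire. A pregnancy test is not among them.

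**The concern.** An exclusion that applies to the whole study should be verified before study drug is given. Here the first specified test comes after the first set of capsules has been dispensed and most or all of it is due to have been taken. Telephone screening and the bar in section IV.D.b can keep out women who know they are pregnant. What remains is unrecognised pregnancy.

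The gap also falls unevenly. The order of treatment is counterbalanced, so half the participants take naltrexone in week 1 and half in week 2. A woman allocated placebo first is tested at visit 2, before her naltrexone week. A woman allocated naltrexone first is not tested before hers. Which of them has the exclusion checked before active drug depends only on a blinded allocation.

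At stake are participant protection and the plan's consistency with its own eligibility criteria. No endpoint, sample size or analysis is affected.

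**Working it through.** The plan gives no figure to reproduce on this point. The check is one of timing and scheduled dose.

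**Inputs**
- Interval from visit 1 to the first MRI at visit 2: 5 days (section IV.C), taken as 5 × 24 = 120 hours.
- Test window: no more than 24 hours before each MRI (section IV.D.b).
- Naltrexone by day of dosing: 25, 25, 50, 50 and 50 mg, once daily with a 9 am reminder (section IV.C.a).
- Sample: "To recruit ~10 participants in one year" (section IV.B.b), half of them on naltrexone in week 1 (section IV.C.a).
- Assumption: the first capsule is taken on the day of visit 1 (day 0) or the day after (day 1). The protocol does not say which.

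**Can the 24-hour rule cover first dispensing?**
Earliest test that meets the rule = 120 − 24 = 96 hours after visit 1, that is, day 4. A test at visit 1 would be about 120 hours before the MRI and would not meet the rule. A site that follows every stated rule can therefore dispense and start dosing before any specified test.

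**Naltrexone scheduled before the test (naltrexone-first half)**
Cumulative dose: 25; 25 + 25 = 50; 50 + 50 = 100; 100 + 50 = 150; 150 + 50 = 200 mg.

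| Test taken | First capsule | Doses before test | Naltrexone before test |
|---|---|---|---|
| Visit 2 (day 5) | Day 0 | 5 | 200 mg |
| Visit 2 (day 5) | Day 1 | 4 or 5 | 150 or 200 mg |
| Day 4 (earliest allowed) | Day 0 | 4 or 5 | 150 or 200 mg |
| Day 4 (earliest allowed) | Day 1 | 3 or 4 | 100 or 150 mg |

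Where two values appear, they depend on whether that day's capsule is taken before or after the test. With the test at visit 2, as section IV.C describes, the range is 150 to 200 mg. The most favourable combination still gives three of five doses, 100 of 200 mg. No combination gives zero.

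**Who is concerned**
Naltrexone-first half: 10 / 2 = 5 participants. The sex split is not stated, so the females among them number 0 to 5. The documents give no rate of unrecognised pregnancy, so no expected number of cases is calculated.

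**The case against.** The strongest reply is that the visit 1 text is a summary, not a full list of procedures. It leaves out at least one step required elsewhere: exclusion C applies a urine drug screen and breathalyzer at the start of every visit, and neither is mentioned for visit 1. Silence about a pregnancy test is then weak evidence that none is planned. A rule about testing before each MRI also does not say that no other test takes place. This has force, and it limits the claim to what is specified: no earlier test is stated. It does not remove the point, because the one timing rule the plan gives cannot be met by a test at first dispensing, and nothing else in the text requires one.

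A second reply is that the documents state no pregnancy hazard for naltrexone, and that the test is explained only under MRI risks, so it is timed to the hazard it addresses. It is true that sections IV.D.d.i and ii list no such hazard, and none is asserted here. But the exclusion itself is written for the study as a whole.

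Third, self-report at the telephone screen covers part of the problem, the visit 2 test covers the second set of capsules, and the consent pages, which are not available, may contain further wording. All of this is accepted. What is left is unrecognised pregnancy during the first course. The numbers are small and may be zero. On the most favourable timing, half of the course by milligrams precedes the test, although that is three of its five doses.

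**Conclusion.** The concern holds for the protocol text available. Pregnancy excludes from the whole study, but the first test the plan specifies comes at least about 96 hours after the first capsules are handed over. In the naltrexone-first half, 100 to 200 mg is scheduled before that test (150 to 200 mg if it is done at visit 2). The result rests on reading the five-day interval as about 120 hours, on one capsule daily, and on a first capsule on day 0 or day 1. It would change only if a test before dispensing is specified in material not available here. The point is modest in scale: at most 5 of about 10 participants, no pregnancy rate assumed, and no effect on any endpoint or analysis. It should still be corrected, because the gap is in the plan's own rules and costs little to close.

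**What to change.** - In section IV.C, add a urine pregnancy test for females at visit 1, with a negative result confirmed before capsules are dispensed. Dispensing is double-blind, so this has to apply to all females and not only to the naltrexone-first half.
- In section IV.D.b, reword the timing rule so that a test is required before first dispensing and, as now, no more than 24 hours before each MRI. The later tests stay necessary, because a visit 1 test finds only what is detectable that day.
- As an editorial matter, list in the visit 1 sequence the drug screen and breathalyzer that exclusion C already requires, and name one specimen for the drug screen throughout (exclusion C says urine, visit 2 says saliva).

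The cost is wording in two places, a few minutes at visit 1, and one extra use per female participant of a test the study already performs: 0 to about 10 tests in all. Blinding, sample size and analysis are unchanged.

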Liver damage or hepatitis is possible. Patients should tell their practitioner about any of the following symptoms during treatment: stomach area pain lasting more than a few days, dark urine, yellowing of the whites of your eyes, tiredness, Practitioners may need to stop treatment using naltrexone if patients develop signs or symptoms of a serious liver problem, Depressed mood, Pneumonia, Serious allergic reactions, Skin rash, swelling of face, eyes, mouth, or tongue, trouble breathing or wheezing, chest pain, feeling dizzy or faint.

iii. Minimizing risk

Remote video monitoring will also be used to assess adherence. Dosing size will be set before participants receiving the naltrexone and participants will start on smaller doses (25mg) for two days before being raised to the final dosing to allow for adjustment to naltrexone and in case of adverse reaction to naltrexone. We will use a questionnaire to check for adverse reactions and will provide care as needed for moderate or severe side effects, such as nausea.

e. Psychological Tests

i. During the Standardized Clinical Interview for the DSM-V (SCID)
participants may discuss negative or traumatic events they have experienced. The SCID will be administered by a trained psychiatrist or by a member of the team trained by the team psychiatrist. Some of the questionnaires may cause emotional distress by asking about traumatic or unpleasant events from a person's life. While most individuals will tolerate this discomfort without problems, it is possible that the memories may trigger unhappiness. To mitigate the risk, study staff will allow participants to take breaks as needed. If serious distress arises, participants will be referred to a psychiatrist from the study team. This protocol may identify mental health problems, such as depression, suicidality, or substance use disorders. Problems with acute danger, such as suicidality will receive immediate attention and intervention. Individuals with diagnoses such as depression or alcohol use disorder will be given referrals for treatment.

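### No side-effect check is scheduled after visit 3, so participants who take naltrexone in week 2 are last asked 0–1 day after their final active capsule (a minor safety improvement, not an error)

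*Combined protocol and SAP*

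**What the plan says.** Section IV.C (Study Design and Research Methods) sets three visits. Capsules are dispensed at visit 1. Then: "Participants will return five days later for visit 2". "On visit 2, they will complete a medication side-effect questionnaire". Anyone reporting more than mild side effects is followed up by a nurse or physician, who clears them for the scan and gives care if needed. A second five-day supply is dispensed, and for the next return (called visit 3 here) the text says: "They will return after 5 days and repeat the same procedures".

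Under Dosing (IV.C.a), the naltrexone week runs "Monday-25mg, Tuesday-25mg, Wednesday-50mg, Thursday-50mg, Friday-50mg", and the order is balanced: "Half of participants will receive placebo during week 1 and half will receive placebo during week 2". Daily reminder texts and uploaded videos accompany the capsules, with adherence as their stated purpose.

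Under Minimizing risk (IV.D.d.iii), the 25 mg lead-in is there "to allow for adjustment to naltrexone and in case of adverse reaction to naltrexone". That section also promises a questionnaire for adverse reactions but gives no time point beyond those in IV.C. The paragraph on liver and other serious effects (IV.D.d.ii) says: "Patients should tell their practitioner about any of the following symptoms during treatment". No call, visit or questionnaire after visit 3 is described.

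**The concern.** In a crossover, the first-period treatment is automatically observed for longer than the second. Here the side-effect questionnaire is tied to the two scan visits, so the length of observation after naltrexone depends on the sequence drawn. One half is asked at the end of the naltrexone week and again a placebo week later. The other half is asked at the end of the naltrexone week and then not again on any described schedule.

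What is at stake is participant safety, not inference. The volunteers are healthy and the protocol expects no direct benefit for them. It lists serious risks of naltrexone, including liver injury. One liver warning sign in IV.D.d.ii, abdominal pain, is defined by how long it lasts, and a check very soon after dosing is poorly placed to establish duration.

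**Working it through.** **Inputs**

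- Returns: five days after visit 1 and five days after visit 2 (IV.C). With visit 1 on day 0, visit 2 is day 5 and visit 3 is day 10.
- Capsules: five per week, once daily (IV.C.a). Capsule 3 is the first at 50 mg and capsule 5 is the last.
- Dose in the naltrexone week: 25 + 25 + 50 + 50 + 50 = 200 mg.
- Participants: 10 (section I), half per order, so 10 / 2 = 5 take naltrexone in week 2.
- Assumption: the first capsule is taken on the day of dispensing or the day after, since IV.C does not say which. A capsule due on a visit day is assumed taken before the visit, in line with the 9 am reminder.

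**Formula**

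Interval = day of visit 3 (10) − day of the capsule in question.

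**Results**

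| First capsule | Naltrexone in | Capsule days | Last active capsule to visit 3 | First 50 mg to visit 3 |
|---|---|---|---|---|
| Day of dispensing | Week 1 | 0–4 | 10 − 4 = 6 days | 10 − 2 = 8 days |
| Day of dispensing | Week 2 | 5–9 | 10 − 9 = 1 day | 10 − 7 = 3 days |
| Next day | Week 1 | 1–5 | 10 − 5 = 5 days | 10 − 3 = 7 days |
| Next day | Week 2 | 6–10 | 10 − 10 = 0 days | 10 − 8 = 2 days |

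Naltrexone in week 2 therefore gives 0–1 day from the last active capsule and 2–3 days from the first 50 mg. Naltrexone in week 1 gives 5–6 and 7–8 days. The difference between sequences is 5 days under either assumption about the first capsule.

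The plan states no figure of its own to reproduce here.

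**Effect of the proposed contact**

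A check 5–7 days after the last capsule would put the week-2 naltrexone group at 5–7 days from the last active capsule. From the first 50 mg it would be 7–9 days, because capsule 3 precedes capsule 5 by 2 days.

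**The case against.** The strongest reply is that nothing in the documents sets a follow-up standard that the plan fails to meet. Every participant is asked in person at the end of the naltrexone week, after all five capsules, with a route to medical care. Both sequences get that check 0–1 day after the last active capsule. The later check for those who take naltrexone first is a by-product of the crossover. Exposure is short, at five capsules and 200 mg in total. All of this stands, and it is why the point is a suggestion and not an error.

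Four stronger readings are tempting, and the documents do not support them.

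- A reader might infer from the weekday labels, together with "They will receive 5 additional capsules to take each day of the following week", that visit 3 falls before the last naltrexone capsules of week 2. IV.C pairs a five-day supply with a five-day return, which most naturally means returning once the supply is used. The background section also relies on scanning at steady state, which an earlier visit would undercut. The weekdays are better read as labels for days 1 to 5.
- A reader might infer that reactions will first appear after visit 3. The documents give no onset times. The duration attached to abdominal pain is not an onset time.
- A reader might infer that the videos have no safety role. Their stated purpose is adherence, but IV.D.d.iii lists them under minimizing risk. What can be said is that they accompany capsule-taking and add no check after visit 3.
- A reader might infer that participants have no way to report later symptoms. The instruction in IV.D.d.ii to report symptoms covers the treatment period, and the consent pages, not available here, may give advice for afterwards.

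**Conclusion.** The point holds as a minor safety improvement. The protocol text describes no scheduled side-effect check after visit 3. For about 5 of 10 participants that leaves 0–1 day of scheduled observation after the last active capsule, against 5–6 days for the other half. These intervals rest on daily capsules starting on the day of dispensing or the next day, and on the stated five-day returns. No planned outcome or analysis is affected, and symptoms already present at visit 3 would be caught and acted on. How many reactions a later check would find cannot be estimated from the documents.

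**What to change.** Add to IV.C, in words such as: *About 5–7 days after the last capsule, every participant, whatever the sequence, will complete the medication side-effect questionnaire remotely by REDCap link or phone. Moderate or severe reports will be passed to the study nurse or physician.*

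Contacting everyone keeps the blind. The window is pragmatic: it roughly matches the 5–6 days that the naltrexone-first group already has, and it is not derived from a risk-onset figure.

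The cost is one or two protocol sentences and about 10 short contacts (10 participants × 1), using the text-message and REDCap arrangements already planned. Participants and the coordinator each give a few minutes per contact. Scans, sample size and planned analyses are unchanged.

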COMIRB Protocol

COLORADO MULTIPLE INSTITUTIONAL REVIEW BOARD
[name] [contact] [contact]

Protocol #: 21-2886

Project Title: Opioid Modulation and Neural Reward Activation in Healthy Adults

Principal Investigator: [name]

Version Date: 10/28/21

I. Hypotheses and Specific Aims:

1. Evaluate whether mu-opioid receptor blockade via naltrexone alters reward activation in the ventral striatum. In a study of 10 healthy, moderate drinking adults, we will use a crossover design to examine brain activation during a functional MRI scan during placebo and mu-opioid blockade.

Hypothesis 1. Relative to the placebo scan, participants will show reduced reward-related activation in the ventral striatum during the active medication scan.

2. Evaluate whether mu-opioid receptor blockade alters threat activation in the amygdala. In the same sample and design from Aim 1, we will use the Emotion Regulation Task to assess threat related activation in the amygdala during a functional MRI scan.

Hypothesis 2. Opioid receptor modulation will not affect threat related activation, consistent with naltrexone primarily targeting reward motivation.

3. Examine whether mu-opioid receptor blockade via naltrexone alters valuation of alcohol. In the same sample and study design from Aim 1, we will use the Alcohol Purchase Task to assess subjective value of an alcoholic beverage in order to link opioid-modulation directly to alcohol motivation.

Hypothesis 3. Relative to the placebo session, participants will be willing to pay less money for an alcoholic beverage during the active medication session.

This proposal aims to fill a gap in understanding how endogenous opioid function affects reward response in the brain. One of the leading hypotheses is that individuals who drink to maximize reward are more likely to benefit from naltrexone treatment, and the current proposal would provide evidence for this in a healthy sample. Further, this work could lead to a clinical study of reward-related brain activation and response to naltrexone treatment in adults with an Alcohol Use Disorder. This stands to improve precision medicine approaches to tailor treatments for alcohol use disorder.

II. Background and Significance:

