- ii. **Emotion Regulation task:** In the emotion regulation task (Waugh et al. 2016), we will examine subjects' ability to change how they are feeling by changing the way they think. Participants will be shown a series of pictures from the International Affective Picture System that have been validated and grouped by rating (e.g. typically induces negative affect) (Lang, Bradley, and Cuthbert 1997). Some pictures are designed to be neutral, such as pictures of nature scenes, and some are designed to evoke strong negative feelings, such as disgust or horror. Prior to viewing each picture, the participant will be instructed to either "Look" or "Decrease". When instructed to "Look", participants are told to keep their eyes on the picture and feel any feelings naturally without trying to change them. This instruction occurs prior to all 15 neutral pictures and prior to 15 of the negative pictures. When instructed to "Decrease" prior to the remaining 15 negative pictures, participants are told to keep their eyes on the picture and find an aspect of it that is not as bad as it seems at first. After viewing each image, participants will be asked how negative they feel. They will be shown a five-point Likert scale from one (not at all) to five (extremely negative), and they will record their response by pressing one of five buttons on a button box attached to their hand. Two sets of pictures will be available so that each participant will see a new set of images on each scan. Order of the sets will be counterbalanced across participants.

[figure not shown]

Figure 3: This figure shows the presentation of the cues for the Social Task used

- iii. **Social Task:** The task, adapted from Jepma et al and Willroth et al, requires participants to rate their expected and experienced valence of varying types of images (Fig. 3). Three distinct geometric shapes acted as cues that predicted the category of image that the individual would subsequently view (erotic, non-erotic pleasant, or neutral). On presentation of the cue, the subject is asked to rate the expected valence of the image using a slider device on a scale of unpleasant to pleasant (coded as 0 to 100). After rating their expectation, they

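### Picture-set order is not stated to be balanced within drug order; with 5/5 splits of both among 10 participants, any difference between the sets shifts the amygdala estimate

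*Combined protocol and SAP*

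**What the plan says.** - **Size.** Section I, Aim 1: "In a study of 10 healthy, moderate drinking adults, we will use a crossover design". Aim 2 uses the same sample and design. The feasibility paragraph (IV.B.b) is looser: "To recruit ~10 participants in one year".
- **Drug order.** IV.C.a (Dosing): "Dosing will be double-blind and counter balanced", and "Half of participants will receive placebo during week 1 and half will receive placebo during week 2". The Investigational Drug Service maintains the blind, and "A study coordinator blind to the contents of the capsules will deliver the capsules to the participant".
- **Picture sets.** IV.C.b.ii (Emotion Regulation task): "Two sets of pictures will be available so that each participant will see a new set of images on each scan", then "Order of the sets will be counterbalanced across participants". The pictures come from a standard collection and are described as ones "that have been validated and grouped by rating".
- **Outcome and analysis.** IV.A takes amygdala percent signal change to negative images as the Aim 2 outcome. IV.F compares the active and placebo sessions by paired t-test. It names no term for picture set.

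The plan does not say how set order relates to drug order, what the numerical split of set order is, or whether the two sets are matched to each other in the response they evoke.

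**The concern.** Each participant sees one set on naltrexone and the other on placebo. If set A evokes a stronger amygdala response than set B by an amount D, each paired difference contains +D or −D, depending on which set was seen on naltrexone. These terms cancel in the mean only if set A falls on naltrexone as often as on placebo. Balancing set against visit, which is what the wording secures, does not guarantee this. The balance that matters is set against drug.

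Hypothesis 2 predicts no drug effect on threat activation, and Section II presents threat as the control paradigm for reward specificity. A shift could show up as a spurious drug effect or offset a real one. In addition, variation between sets that the analysis ignores widens the paired SD and makes the predicted null result easier to obtain.

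**Working it through.** The plan gives no figure for set balance, so there is none to reproduce on this point. Its one related figure is the sample size in IV.F: 9 adults for d = 1.0, two-sided 0.05, 80% power. The exact paired t-test gives 74.8% at 9 and 80.3% at the planned 10. Nothing below depends on this.

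**Inputs.** N = 10 (Section I). Drug order 5/5 (halves, IV.C.a). Set order 5/5 (assumed: the natural reading of counterbalancing at N = 10, but not stated). D = mean set A minus set B amygdala response (not in the documents).

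**Step 1: possible splits.** Let k be the number of naltrexone-first participants who see set A first.

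- The naltrexone-first group has k participants with set A on naltrexone.
- The placebo-first group has 5 − k participants with set A first, that is, on placebo. The other 5 − (5 − k) = k see set A on naltrexone.
- Total with set A on naltrexone = 2k, and on placebo = 10 − 2k.

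Equal mixes need 2k = 5, which no whole number satisfies.

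**Step 2: shift.** Shift in the mean paired difference = D × [2k − (10 − 2k)]/10 = D(4k − 10)/10.

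**Step 3: chances.** If set order is drawn independently of drug order, P(k) = C(5,k)²/C(10,5), with C(10,5) = 252.

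| k | Set A on naltrexone : placebo | Shift | Chance |
|---|---|---|---|
| 2 or 3 | 4:6 or 6:4 | ∓0.2D | 200/252 = 79.4% |
| 1 or 4 | 2:8 or 8:2 | ∓0.6D | 50/252 = 19.8% |
| 0 or 5 | 0:10 or 10:0 | ∓1.0D | 2/252 = 0.8% |

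The distribution is symmetric, so the mean shift over allocations is zero.

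**Step 4: effect on the test.** Simulated two-sided type I error at nominal 5%, N = 10, no drug effect. D is in units of the paired-difference SD that would be seen without a set effect (assumed values):

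| Split | D = 0.2 | D = 0.5 | D = 1.0 |
|---|---|---|---|
| 5:5 (for reference) | 4.60% | 2.93% | 0.68% |
| 6:4 | 4.67% | 3.72% | 1.66% |
| 8:2 | 6.02% | 10.58% | 20.10% |
| 10:0 | 8.74% | 29.30% | 80.20% |

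Weighted by the chances in Step 3:

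- D = 0.2: 0.794 × 4.67 + 0.198 × 6.02 + 0.008 × 8.74 ≈ 5.0%
- D = 0.5: 0.794 × 3.72 + 0.198 × 10.58 + 0.008 × 29.30 ≈ 5.3%
- D = 1.0: 0.794 × 1.66 + 0.198 × 20.10 + 0.008 × 80.20 ≈ 5.9%

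**Step 5: size in the usual case.** The standard error of the mean paired difference is 1/√10 = 0.316 SD. At 6:4 with D = 0.5 SD the shift is 0.2 × 0.5 = 0.10 SD, or 0.10/0.316 ≈ 0.3 of a standard error. At 8:2 it is 0.6 × 0.5 = 0.30 SD, close to one standard error.

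**Step 6: the alternative list.** With 3 A-first and 2 B-first in each drug order, set A is seen on naltrexone by 3 (naltrexone-first, A-first) + 2 (placebo-first, B-first) = 5, and on placebo by 2 + 3 = 5. The shift is zero. If one participant is lost, the split is 5:4 and the shift is D × (5 − 4)/9 ≈ 0.11D.

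**The case against.** **Silence is not a design choice.** A reader might infer that the two orders are definitely uncrossed, or that blinded staff could not cross them. The documents support neither. They do not say who prepares either list, and the Investigational Drug Service could cross the orders without unblinding anyone. What stands is that the link is not written down. The parity result would also survive the closest possible 5/5-by-5/5 balancing, because 5 is odd.

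**Full confounding is not the expected case.** A reader might suppose that both orders could be alternated by enrolment number, so that one set always falls on naltrexone. Section IV.E describes the design as randomised, and strict alternation of drug order is not randomisation. With independent allocation, full confounding has a chance of 0.8%.

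**The harm is modest on average.** The sign is random, so this is chance imbalance and not a systematic bias. Average type I error is close to nominal, and at 6:4 it is below nominal. This objection stands in full. It does not cover the one trial in five at 8:2 or worse (52/252 = 20.6%).

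**D may be small.** The pictures are validated and grouped by rating, and each scan uses 30 negative pictures (15 with each instruction). Both facts bear on how large D could be. Neither says that the two sets are equivalent in amygdala response.

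**Exactly 10 completers is an assumption.** Recruitment is approximate, and a positive drug or alcohol test at any visit is an exclusion, so losses after allocation are possible. With 8 or 12 completers and equal halves, exact balance is attainable (2 or 3 per cell), but the plan does not direct anyone to achieve it.

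**Conclusion.** The concern holds as a gap in the written allocation that is cheap to close. The plan does not state that set order is balanced within drug order, and the analysis would not remove a set difference. With exactly 10 participants and 5/5 splits of both orders, the drug conditions cannot receive the same picture mix. The amygdala estimate then moves by 0.2D (about 79%), 0.6D (about 20%) or 1.0D (under 1%) under independent allocation.

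At the usual 6:4 split the cost is a small shift and a wider paired SD, with no inflation of type I error. Inflation arises at 8:2 or worse, for example to 10.6% at 8:2 if D is 0.5 SD.

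This rests on three things that the documents do not settle: a 5/5 set split, exactly 10 completers, and a non-zero D. If the sets are equivalent, there is no shift. The documents do not support a claim that Aim 2 is systematically biased or that its result would be invalid.

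**What to change.** Replace the sentence on set order in IV.C.b.ii with, for example:

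> *Set order is assigned jointly with drug order from a single list held by the Investigational Drug Service, which gives the site only the set code for each visit. Within each drug order, three participants see set A first and two see set B first.*

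Each drug then gets set A in 5 participants and set B in 5, drug order stays 5/5, and the blind is kept.

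Add to IV.F a sensitivity analysis for the amygdala outcome with a set term: regress the paired difference on an indicator coded +1 if set A was seen on naltrexone and −1 otherwise, and read the drug effect from the intercept. This covers dropout. It also removes the extra variance that the balanced list alone leaves in the paired t-test (the 5:5 row in Step 4). The variance cost of the term is 1/(1 − m²), where m is the mean of the indicator: 1/(1 − 0.04) = 1.042, or 4.2%, at 6:4, and none at 5:5, apart from one degree of freedom.

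**Cost.** Two short edits and one extra column on the pharmacy list, with no added visits or participants. Set order overall becomes 6/4, which does not bias the drug comparison because it is the same in both drug orders. Exact balance holds only with 10 completers; one loss leaves a shift of about 0.11D.
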